3.2.1.2.9 Treatment acceptability

The treatment acceptability at the time of intake after dose 1 and after dose 2 will be assessed by a Treatment Acceptability Questionnaire completed by the caregiver or the subject using a

5-point scale questionnaire (see Table 4). It will be tabulated for each dose and overall (by taking the average of the 2 doses then considered as a score as follows: 1= Very badly accepted/unacceptable, 2= Badly but accepted, 3= Neither good nor bad, 4= Well accepted and 5= Very well accepted) by treatment group.

The acceptability for each dose will be assessed using frequency count with two-sided 95 % CI and analysed using Cochran-Mantel-Hænszel (CMH) chi-square for the proportions adjusting for country effect. The row mean scores differ statistic will be used to assess the test significance.

The SAS Freq procedure will be used as follows:

```
proc freq data=ADQS(where=(QSCAT='TREATMENT ACCEPTABILITY
QUESTIONNAIRE' and PARAMCD in ('TRTA011','TRTA012') and ITTFL='Y'));
table COUNTRYC*TRTP*QSORRES / CMH;
by QSGRPID;
```

run;

The p-value of difference will be summarised.

The overall acceptability will be presented by treatment group using descriptive summary statistics (mean, SD, median, quartiles and ranges) and using a two-way ANOVA including treatment and country as well as the interaction between treatment and country, if it is significant (i.e. p < 0.10), as covariates using the following SAS code:

```
proc mixed data=ADQS(where=(QSCAT='TREATMENT ACCEPTABILITY QUESTIONNAIRE' and PARAMCD='TRTA01' and ITTFL='Y'));
```

```
class TRTP COUNTRYC;
model COMPLIPCT = TRTP COUNTRYC TRTP*COUNTRYC;
by ASPID;
```

lsmeans TRTP / diff cl;

run;

The adjusted mean score, the adjusted treatment difference with their 95 % CI and the p-value of difference will be summarised.

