proc mixed data= ADEX(where=(EXCAT='COMPLIANCE' and EXSCAT='Overall' and ITTFL='Y'));

class TRTP COUNTRYC SUBGROUP;

model COMPLIPCT = TRTP COUNTRYC SUBGROUP TRTP*SUBGROUP; lsmeans TRTP*SUBGROUP / diff cl;

run;

Additionally, a subject will be considered as compliant with the instructions of use provided in the prescription if he/she drinks the whole preparation (volume = 100 %). The proportion of subjects compliant with the instructions of use provided in the prescription will be presented using summary statistics with the 95 % CI by treatment group and analysed using Cochran-Mantel-Hænszel (CMH) chi-square for the proportions adjusting for country effect. The general association statistic will be used to assess the test significance.

The SAS Freq procedure will be used as follows:

```
proc freq data=ADEX(where=(EXCAT='COMPLIANCE' and EXSCAT='Overall' and ITTFL='Y'));
```

table COUNTRYC*TRTP*COMPLI / CMH; by ASPID;

run;

The difference of proportions with the 95 % CI and p-value will be summarised.

Finally, the compliance will be presented by categories (100 %,]100-75],]75-50] and < 50 %). The proportion of subjects in each category will be presented using summary statistics with the 95 % CI by treatment group and analysed using Cochran-Mantel-Hænszel (CMH) chi-square for the proportions adjusting for country effect. The row mean scores differ statistic will be used to assess the test significance.

The SAS Freq procedure will be used as follows:

proc freq data=ADEX(where=(EXCAT='COMPLIANCE' and EXSCAT='Overall' and ITTFL='Y')); table COUNTRYC*TRTP*COMPLICL / CMH; by ASPID;

run;

The difference of proportions with the 95 % CI and p-value will be summarised.

The percentage of compliance, the proportion of patients considered as compliant and the compliance in categories will be described after each dose and overall. For the Eziclen/Izinova treatment group, the compliance will be also described separately for active treatment and hydration after each dose and overall.

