3.2.1.3.3 Satisfaction

The satisfaction will be also assessed through the question "If it was necessary, would you agree to undergo preparation with this product again?". It will also be tabulated by treatment group using frequency count with two-sided 95 % CI and analysed using Cochran-Mantel-Hænszel (CMH) chi-square for the proportions adjusting for country effect. The general association statistic will be used to assess the test significance.

The SAS Freq procedure will be used as follows:

```
proc freq data=ADQS(where=(QSTEST='AGREE TO TAKE PRODUCT AGAIN' and ITTFL='Y'));
```

table COUNTRYC*TRTP*QSORRES / CMH;

run;

The difference of proportions with the 95 % CI and p-value will be summarised.

3.2.1.3.4 Time between the last intake of fluids and the start of colonoscopy procedure

The time between the last intake of fluids and the start of colonoscopy procedure will be presented by treatment group using descriptive summary statistics (mean, SD, median, quartiles and ranges) and using a two-way analysis of variance (ANOVA) including treatment and country as well as the interaction between treatment and country, if it is significant (i.e. p < 0.10), as covariates using the following SAS code:

proc mixed data=ADEX(where=(PARAM='Time between the last intake of fluids and the start of colonoscopy procedure' and ITTFL='Y'));

class TRTP COUNTRYC;

38/62

model AVAL = TRTP COUNTRYC TRTP*COUNTRYC;
lsmeans TRTP / diff cl;

run;

The adjusted mean times, the adjusted treatment difference with their 95 % CI and the p-value of difference will be summarised.

In addition, this analysis will also be produced per country so that mean scores and the estimated treatment differences will also be provided per country using the following SAS code.

proc mixed data=ADEX(where=(PARAM='Time between the last intake of fluids and the start of colonoscopy procedure' and ITTFL='Y'));

```
class TRTP COUNTRYC;
model AVAL = TRTP COUNTRYC TRTP*COUNTRYC;
lsmeans TRTP*COUNTRYC / diff cl;
```

run;

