A subject is considered as compliant with the instructions of use if he/she drinks the whole preparation (100% of compliance) and any required further fluid intake (100% of compliance).

The planned volume is 750 mL for Eziclen (375 mL per dose), 1500 mL for hydration (750 mL per dose) and 70 mL/kg for Klean-Prep® with a maximum of 4000 mL (maximum 2000 mL per dose).

(12) Compliance in class

The compliance in class is defined from the compliance in percentage as follows:

- 100 %,
-]100-75],
-]75-50],
- < 50 %.
- (13) Lesions caused by colonic lavage

Histological examination results of lesions caused by colonic lavage will be identified among the adverse events by looking for the term "colonic lavage" in the verbatim term, since the investigator should identified the suspected lesions using "suspected to have been caused by colonic lavage". The occurrence (Yes/no) will then be derived for each subject.

(14) Baseline

Baseline will be derived as the last available assessment before administration of the IMP.

(15) Changes from baseline

Changes from baseline will be calculated as a difference from baseline (e.g. assessment at the visit – assessment at baseline).

(16) Therapeutic Class.

The therapeutic class will correspond to the first 3 digits of the ATC code. The decoding of the therapeutic class will be done from the WHO-DD (current version at the time of database lock).

(17) Prior and concomitant flags

The date of first administration of study treatment (study day 1) is used as the cut-off date for the definition of prior and concomitant medications. A drug started before study day 1 and continuing at time of Day 1 is considered as both, prior and concomitant. Prior, concomitant and both prior and concomitant will be coded as P, C and PC respectively.

(18) Concomitant therapy duration

If times are available, the duration of concomitant treatments will be calculated as (end date/time - start date/time). If at least one time is missing, the duration of concomitant treatments will be calculated as (end date - start date) + 1. If the recorded end date is continuing at the end of the study then the end date will be listed as "ongoing" and the duration will be approximated as " \geq (last attended visit date - start date) + 1" day(s). If the start date or the end date are partial, the duration will be presented as an inequality " \geq xx" day(s) [i.e. \geq 2 where start date=31JAN2004 and end date=FEB2004 or start date=JAN2004

51/62

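### The ordinal tests of per-dose acceptability and compliance class do not fix the category order; if text labels are stored, default sorting scrambles both scales

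*SAP*

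**What the plan says.** For acceptability after each dose, SAP 3.2.1.2.9 prescribes a CMH analysis adjusted for country and states: "The row mean scores differ statistic will be used to assess the test significance". The code is "table COUNTRYC*TRTP*QSORRES / CMH". A numeric scale appears in the same section: "1= Very badly accepted/unacceptable, 2= Badly but accepted, 3= Neither good nor bad, 4= Well accepted and 5= Very well accepted". It is attached to the overall score, which is the average of the two doses. SAP Table 4 lists the five categories in order but without numbers.

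For compliance class, SAP 3.2.1.2.10 says "the compliance will be presented by categories (100 %,]100-75],]75-50] and < 50" %, again with the row mean scores statistic. The code is "table COUNTRYC*TRTP*COMPLICL / CMH; by ASPID". Item 12 of Appendix 1 introduces the classes with "The compliance in class is defined from the compliance in percentage as follows" and lists the same four labels without a numeric code.

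Neither call has an ORDER= option, although the primary analysis code in 3.2.1.1 uses order=data. SAP 3.1.5 makes all secondary tests descriptive.

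**The concern.** For its binary outcomes the SAP uses the general association statistic, which ignores category order. At these two places it chooses the row mean scores statistic, which compares mean scores between arms and so depends on which score each category receives. The choice shows that an ordinal test is intended, but the code leaves the scores to the software.

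There are signs, though no proof, that the variables hold text. Other code blocks analyse AVAL, whereas this one uses QSORRES. In 3.2.1.3.3 the same column also holds the answer to the question on taking the product again ("QSTEST='AGREE TO TAKE PRODUCT AGAIN"). COMPLICL is defined only by its labels.

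Comparing acceptability and assessing compliance are stated secondary objectives, and protocol 1.4 cites the lower volume as a reason to expect better willingness to complete the preparation. A programmer who followed the code literally would get a plausible p-value and no error message. SAP 4.3 requires double programming only for the primary endpoint.

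**Working it through.** **Inputs.** The labels come from SAP Table 4 and Appendix 1 (12), and the statistic and code from 3.2.1.2.9 and 3.2.1.2.10. SAP 4.1 gives a Windows PC, hence ASCII sorting. One input is general SAS behaviour and not SAP text: by default PROC FREQ sorts a character column by its stored values and uses the column number as the score. All response distributions below are assumed.

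**Sample size used for illustration.** The plan's figure reproduces: (1.960 + 1.282)² × 2 × 0.85 × 0.15 / 0.15² = 119.1, so 120 per group, and 120 / 0.96 = 125. It serves here only to size the examples.

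**Step 1: scores if the labels are stored**

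| Acceptability label | Intended | Sorted |
|---|---|---|
| Very badly accepted/unacceptable | 1 | 3 |
| Badly but accepted | 2 | 1 |
| Neither good nor bad | 3 | 2 |
| Well accepted | 4 | 5 |
| Very well accepted | 5 | 4 |

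| Compliance label | Intended | Sorted |
|---|---|---|
| 100 % | 4 | 1 |
| ]100-75] | 3 | 3 |
| ]75-50] | 2 | 4 |
| < 50 % | 1 | 2 |

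The absolute correlation between intended and sorted scores is 0.60 for acceptability and 0.40 for compliance. A simple reversal would be harmless; this is not one. Upper-case acceptability labels, or '<50 %' without the space, sort the same way. Stored digits 1 to 5 sort correctly.

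**Step 2: single-stratum examples, 120 per arm.** Q = d² / (v × 2/n) on 1 df, where d is the difference in mean score and v the pooled score variance with divisor N − 1 (N = 240).

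*Acceptability*, from very badly to very well: Eziclen 5/25/35/25/10%, Klean-Prep 25/20/25/20/10%.
- Intended scores: means 3.10 and 2.70, v = 1.446, Q = 0.40² / (1.446 × 2/120) = 6.64, p = 0.010.
- Sorted scores: means 2.75 and 2.85, v = 2.169, Q = 0.10² / (2.169 × 2/120) = 0.28, p = 0.60.

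*Compliance*, from 100% down to below 50%: 80/15/3/2% against 70/10/5/15%.
- Intended: means 3.73 and 3.35, v = 0.842, Q = 0.38² / (0.842 × 2/120) = 10.29, p = 0.0013.
- Sorted: means 1.41 and 1.50, v = 0.741, Q = 0.09² / (0.741 × 2/120) = 0.66, p = 0.42.

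*Compliance with high completion*, Eziclen 93/4/2/1%:
- against 85/8/4/3%: p = 0.059 intended, 0.073 sorted;
- against 80/12/5/3%: p = 0.010 intended, 0.006 sorted.

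**Step 3: stratified simulation.** Four assumed countries of 30 + 30, 4,000 replicates, two-sided 5%.

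| Assumed pattern | Rejection, intended | Rejection, sorted |
|---|---|---|
| Acceptability, shift across the whole scale | 95% | 76% |
| Acceptability, fewer 'very badly', more 'badly' and 'neither' | 48% | 32% |
| Acceptability, 'well' moved to 'very well' | 28% | 18% |
| Compliance, fewer below 50%, more ]100-75] | 53% | 26% |
| Compliance, more at 100% | 67% | 72% |
| No difference (both scales) | 4–5% | 5% |

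Type I error is unaffected, because any fixed set of scores gives a valid test of no difference.

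**The case against.** The strongest reply is that the stored values are unknown. The SAP never says that QSORRES or COMPLICL holds words, and the coding may be settled in a dataset specification or table templates that are not among these documents. The intended scale is also not in doubt: an average over two doses presupposes a numeric score for each dose, both sets of categories are listed in order, and naming the row mean scores statistic signals an ordinal analysis. Some other code blocks are plainly schematic. All of this stands, and it makes the point conditional. It does not remove it, because the printed code does not use the score that the text defines.

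The stakes are also limited. Compliance is analysed as a percentage by ANOVA and as complete or not by CMH, and neither depends on class order. Protocol 5.2.2 provides a nasogastric tube for subjects who cannot finish, and protocol 1.4 reports completion of at least 93% for the 1-day regimen in adults. With completion that high, the class test mostly contrasts 100% with everything else, and order matters little. This stands for compliance; it does not help acceptability.

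A reader might infer from the means in the examples that the test would report a reversed difference. The documents do not support that. The chi-square has no sign, 3.2.1.2.9 reports only its p-value for the per-dose comparison, and direction would be read from frequency tables that category order cannot alter. A reader might also expect the overall acceptability ANOVA to serve as a correctly ordered cross-check. Its text describes the 1–5 score, but its printed code models COMPLIPCT, the compliance percentage, so that cannot be relied on either.

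**Conclusion.** The point holds in conditional form. Two order-dependent tests are prescribed with code that does not fix the order. If the stored values are the printed labels, the p-values refer to scrambled scales; if they are digits or ordered numeric codes, there is no error. It would go too far to say that the scales are scrambled, since no part of the SAP gives the stored values.

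Where it applies, the usual effect is lost power. For acceptability the loss can be large (p = 0.010 against 0.60; rejection 95% against 76%). For compliance it ranges from substantial (53% against 26%) to none (67% against 72%), and it is small when most subjects complete the preparation. These sizes rest on assumed distributions, an assumed number of countries and default SAS sorting. Only descriptive secondary p-values are affected, and the primary non-inferiority conclusion is untouched. The point merits correction because the remedy costs almost nothing.

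**What to change.** In the per-dose code of SAP 3.2.1.2.9, replace QSORRES by the numeric 1–5 score already defined in that section, and say in the text that the scale applies to each dose as well as to the average. In 3.2.1.2.10, replace COMPLICL by an ordered numeric class code, with 1 for below 50%, 2 for ]75-50], 3 for ]100-75] and 4 for 100%, and add that code to Appendix 1 (12). Show the labels through a format.

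The cost is two variable names and two short sentences. No new data are needed, and the change does no harm if the coding is already numeric. While 3.2.1.2.9 is open, the COMPLIPCT reference in the overall acceptability code should be reconciled with the text.

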3.2.1.2.10 Treatment compliance

According to the instructions of use provided in the prescription, subjects should get for Eziclen®/Izinova® 750 mL of preparation followed by an additional 750 mL of water at first and second dose, that is to say a total volume of 2250 mL, and for Klean-Prep® 70 mL/kg of preparation according to the weight split into 2 doses with a maximum global volume administered of 4000 mL (2000 mL per dose). The volumes taken will be presented by treatment group using descriptive summary statistics (mean, SD, median, quartiles and ranges). No comparison will be performed since treatment administration schemes are different.

The treatment compliance will be assessed as the percentage of volume of fluid taken relative to the planned volume of fluid to be taken using the volumes of fluids measured by the caregiver and reported in the treatment questionnaire of subject's leaflet during treatment administration by dose and overall for the preparation for Klean-Prep® and for the preparation, the water and the total for Eziclen®/Izinova®. Then the percentage of compliance will be presented by treatment group using descriptive summary statistics (mean,

SD, median, quartiles and ranges) and using a two-way ANOVA including treatment and country as well as the interaction between treatment and country, if it is significant (i.e. p < 0.10), as covariates using the following SAS code:

proc mixed data=ADEX(where=(EXCAT='COMPLIANCE' and EXSCAT='Overall' and ITTFL='Y'));

class TRTP COUNTRYC;

model COMPLIPCT = TRTP COUNTRYC TRTP*COUNTRYC; by ASPID; lsmeans TRTP / diff cl;

run;

The adjusted mean compliances, the adjusted treatment difference with their 95 % CI and the p-value of difference will be summarised.

In addition, this analysis will also be produced per country so that mean compliances and the estimated treatment differences will also be provided per country using the following SAS code.

proc mixed data= ADEX(where=(EXCAT='COMPLIANCE' and EXSCAT='Overall' and ITTFL='Y'));

class TRTP COUNTRYC; model COMPLIPCT = TRTP COUNTRYC TRTP*COUNTRYC; lsmeans TRTP*COUNTRYC / diff cl;

run;

Moreover, this analysis will also be produced per sex, age class and weight class, so that mean compliances and the estimated treatment differences will also be provided per subgroup using the following SAS code and adding the treatment*country interaction if it is significant.

proc mixed data= ADEX(where=(EXCAT='COMPLIANCE' and EXSCAT='Overall' and ITTFL='Y'));

class TRTP COUNTRYC SUBGROUP;

model COMPLIPCT = TRTP COUNTRYC SUBGROUP TRTP*SUBGROUP; lsmeans TRTP*SUBGROUP / diff cl;

run;

Additionally, a subject will be considered as compliant with the instructions of use provided in the prescription if he/she drinks the whole preparation (volume = 100 %). The proportion of subjects compliant with the instructions of use provided in the prescription will be presented using summary statistics with the 95 % CI by treatment group and analysed using Cochran-Mantel-Hænszel (CMH) chi-square for the proportions adjusting for country effect. The general association statistic will be used to assess the test significance.

The SAS Freq procedure will be used as follows:

```
proc freq data=ADEX(where=(EXCAT='COMPLIANCE' and EXSCAT='Overall' and ITTFL='Y'));
```

table COUNTRYC*TRTP*COMPLI / CMH; by ASPID;

run;

The difference of proportions with the 95 % CI and p-value will be summarised.

Finally, the compliance will be presented by categories (100 %,]100-75],]75-50] and < 50 %). The proportion of subjects in each category will be presented using summary statistics with the 95 % CI by treatment group and analysed using Cochran-Mantel-Hænszel (CMH) chi-square for the proportions adjusting for country effect. The row mean scores differ statistic will be used to assess the test significance.

The SAS Freq procedure will be used as follows:

proc freq data=ADEX(where=(EXCAT='COMPLIANCE' and EXSCAT='Overall' and ITTFL='Y')); table COUNTRYC*TRTP*COMPLICL / CMH; by ASPID;

run;

The difference of proportions with the 95 % CI and p-value will be summarised.

The percentage of compliance, the proportion of patients considered as compliant and the compliance in categories will be described after each dose and overall. For the Eziclen/Izinova treatment group, the compliance will be also described separately for active treatment and hydration after each dose and overall.

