Appendix 1 Derived data

The following derived data will be calculated:

(1) Treatment group

Treatment groups will be defined as "Eziclen/Izinova" and "Klean-Prep".

(2) Study duration

Study duration (days) will be calculated as (last visit attended - date of informed consent) + 1.

- (3) Successful treatment preparation
- A successful preparation will be derived from a colon cleansing scored as excellent (4) or good (3).
- A failure preparation will be defined as:
 - Fair (2) or poor (1) according to colon cleansing score,
 - Any subject who did not have a colonoscopy based on the investigator's assessment of the cleansing (insufficient faecal output, unclear faecal discharge, etc.) or due to preparation related AEs,
 - Any subject for whom cleaning was not adequate for evaluation,
 - Any subject for whom rescue treatment (saline enema) was needed.

(4) Time to clear effluent

It is defined as the time (expressed in hours) from the first intake of prescription to the first clear watery stool occurrence if any, or to the time of colonoscope introduction, if no clear watery stool is observed before the beginning of the procedure and then the time will be considered as censored for the survival analysis. See section 3.2.1.2.3.

(5) Completion of the procedure

"Yes" if the colonoscopy reached the caecum and the item "Was physician able to reach the caecum?" is "Yes", "No" otherwise.

(6) Duration of the intubation

It is defined as the time (expressed in minutes) from colonoscope introduction to caecal intubation.

(7) Duration of the examination

It is defined as the time (expressed in minutes) from caecal intubation to colonoscope withdrawal.

(8) Need of a rescue treatment

"Yes" if a rescue medication was administered and the item "Was any enema needed to achieve preparation?" is "Yes", "No" otherwise.

(9) Need of a nasogastric tube to complete preparation

"Yes" if a nasogastric tube was inserted and the item "Was a nasogastric tube inserted?" is "Yes" at dose 1 or dose 2, "No" otherwise.

(10) Compliance in percentage

The percentage of compliance is defined as (planned volume - residual volume) / planned volume, adding up the solution and water volume where applicable.

50/62

The planned volume is 750 mL for Eziclen (375 mL per dose), 1500 mL for hydration (750 mL per dose) and 70 mL/kg for Klean-Prep® with a maximum of 4000 mL (maximum 2000 mL per dose).

(11) Compliance with the instructions of use

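### The per-country and per-subgroup compliance models drop the BY statement used by the main compliance analysis, so they do not repeat it and may pool several records per subject

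*SAP*

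**What the plan says.** SAP 3.2.1.2.10 (Treatment compliance) calculates compliance "by dose and overall for the preparation for Klean-Prep® and for the preparation, the water and the total for Eziclen®/Izinova". Appendix 1, item 10, also defines a compliance percentage obtained by "adding up the solution and water volume where applicable".

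Five modelling blocks follow, all on the overall compliance records of the ITT population in `ADEX`, for example "proc mixed data= ADEX(where=(EXCAT='COMPLIANCE' and EXSCAT='Overall' and ITTFL='Y". They fall into two groups.

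- **With a BY statement:** the main ANOVA, "model COMPLIPCT = TRTP COUNTRYC TRTP*COUNTRYC; by ASPID; lsmeans TRTP / diff cl", and both CMH tests. The CMH test for full compliance reads "table COUNTRYC*TRTP*COMPLI / CMH; by ASPID", and the one for compliance categories has the same form.
- **Without a BY statement:** the per-country ANOVA, "class TRTP COUNTRYC; model COMPLIPCT = TRTP COUNTRYC TRTP*COUNTRYC; lsmeans TRTP*COUNTRYC / diff cl", and the ANOVA by sex, age class and weight class, "model COMPLIPCT = TRTP COUNTRYC SUBGROUP TRTP*SUBGROUP; lsmeans TRTP*SUBGROUP / diff cl". Neither has a REPEATED, RANDOM or subject term.

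The text introduces both blocks in the second group as the same analysis, also produced per country or per subgroup. SAP 3.1.5 makes all secondary endpoint tests descriptive.

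**The concern.** A BY statement has a purpose only if its variable takes more than one value in the selected data. Three blocks use it and two do not, on one filter, so either the BY is redundant in three blocks or it is missing from two.

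If it is missing, the country and subgroup models stack several records from the same adolescent and count each as a separate observation. Two things follow. The Eziclen mean can become a blend that the SAP defines nowhere, compared with Klean-Prep preparation alone. The standard errors then rest on a wrong count of independent observations and on a residual that mixes variation between subjects with variation between record types.

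Assessing compliance is a stated secondary objective. The country and subgroup tables would not reconcile with the main compliance table, and a reader could take the mismatch for a real country, age, weight or sex pattern.

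**Working it through.** **1. Code comparison.** For the cleansing score (3.2.1.2.1), BBPS (3.2.1.2.2), examination duration (3.2.1.2.6) and time since last fluid intake (3.2.1.3.4), the per-country code repeats the main model and changes only the LSMEANS line. In the compliance section the per-country code also loses the BY statement. The discrepancy is therefore visible in the text, whatever the data look like.

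**2. What the extra records could be.** The SAP does not say. The filter already selects overall records, so the dimension left in the text is preparation, water and total for Eziclen, with preparation only for Klean-Prep. A dose index (dose 1, dose 2, overall) is the other possibility.

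**3. Effect on the mean, component case.** From Appendix 1: "The planned volume is 750 mL for Eziclen (375 mL per dose), 1500 mL for hydration (750 mL per dose"). The planned total is 750 + 1500 = 2250 mL, so total compliance = (preparation + 2 × water)/3. Assume 90% of the preparation and 70% of the water are taken:

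- total = (0.90 × 750 + 0.70 × 1500)/2250 = 1725/2250 = 76.7%
- pooled mean = (90 + 70 + 76.7)/3 = 78.9%

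The pooled figure is neither preparation, water nor total. In the dose case the planned halves are equal, so the mean of dose 1, dose 2 and their average is the overall value again; only the precision would suffer.

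**4. Effect on the interval, component case.** The documents give no SD, mean or correlation for compliance, so these are assumptions: SD 10 in both arms, n subjects per arm in a cell, preparation-water correlation ρ, three Eziclen records and one Klean-Prep record per subject. Variances are in units of SD². Large-sample algebra at ρ = 0.5 with equal means gives:

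- Subject mean of the three records = (4 × preparation + 5 × water)/9, with variance (41 + 40ρ)/81 = 61/81 = 0.753. True variance of the arm difference = (0.753 + 1)/n = 1.753/n.
- Variance of the total = (5 + 4ρ)/9 = 0.778. Average Eziclen record variance = (1 + 1 + 0.778)/3 = 0.926. Residual variance pooled over 3n + n records = (3 × 0.926 + 1)/4 = 0.944.
- Model variance of the difference = 0.944 × (1/(3n) + 1/n) = 1.259/n.
- Model SE / true SE = √(1.259/1.753) = 0.85, so the interval is too narrow.

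Now let mean water compliance be 20 points (2 SD) lower. The component means relative to preparation are 0, -2 and -1.333, with a between-record spread of 0.691. The Eziclen record variance becomes 0.926 + 0.691 = 1.617, the residual (3 × 1.617 + 1)/4 = 1.463, and the model variance 1.951/n. The ratio is √(1.951/1.753) = 1.05. At 30 points the spread is 1.556 and the same steps give 1.27.

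Simulation (60 per arm per cell, which is also an assumption; 1500 replicates; ρ from 0 to 1) agrees:

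| Water relative to preparation | Model SE / true SE, difference | 95% CI coverage |
|---|---|---|
| equal mean and SD | 0.79-0.88 | about 88-92% |
| 5 points lower | 0.81-0.89 | about 88-92% |
| 20 points lower | 1.01-1.12 | about 95-98% |
| 30 points lower | 1.23-1.38 | about 99% |

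Coverage is measured around the pooled quantity. That quantity is itself shifted: with water 20 points lower and true preparation compliance equal in both arms, the pooled difference is -11.1 points against -13.3 for the total. For the Eziclen mean alone, with equal means and SDs, the SE ratio is 0.57-0.77 and coverage about 73-88%.

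**5. One record per subject.** The usual SE applies and the missing BY changes nothing.

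**The case against.** The strongest reply is that pooling is not shown. The SAP never defines `ASPID` and never states how many overall records a subject has. Appendix 1 can be read as giving one summed percentage per subject, and 3.2.1.2.10 ends by saying that active treatment and hydration are also described separately, which could mean an extra listing beside a single combined record. The same BY statement appears in the overall acceptability ANOVA (3.2.1.2.9), where each subject has one averaged score, so its presence is not proof of several records. The dataset specification is not in the documents.

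This stands as far as it goes, and the point is conditional for that reason. The acceptability block is weak evidence about `ADEX`, however: it names the compliance percentage as its outcome and looks like pasted code. If `ASPID` were constant, the BY in three compliance blocks would do nothing.

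A second reply is that the intent is clear and the checks in SAP 4.3 (observation counts, cross-checks between outputs) should catch stacked records. They may, but only the primary endpoint must be double-programmed, and it is better to correct the specification than to rely on later detection.

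A reader might also infer that the intervals are always too narrow, or that the nominal 5% error roughly quadruples. The first fails once water compliance is well below preparation compliance, including at the 20-point gap used above for the mean. The second (simulated at 18-20%) needs two Klean-Prep records per subject, and the compliance text lists only the preparation for that arm.

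**Conclusion.** The inconsistency is established: two of the five compliance blocks omit a BY statement that the other three use on the same filter, so as printed they do not repeat the main analysis. The consequence is conditional. If the filter leaves several records per subject, correlated records are analysed as independent. In the component case the Eziclen mean is then a blend, and interval coverage for the treatment difference runs from about 88% to about 99% depending on how far water compliance falls below preparation compliance. These figures rest on the assumed SD, correlation, means and cell size. If there is one record per subject, the effect is nil.

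The documents do not support the flat statement that records are pooled or that the intervals are too narrow. The reach is limited to descriptive secondary compliance tables by country, sex, age class and weight class. It is worth correcting because it is a definite specification slip with an almost free remedy.

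**What to change.** In SAP 3.2.1.2.10:

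1. Define `ASPID` and state how many overall compliance records each subject has in `ADEX`, by arm.
2. Name the single compliance record per subject used for the between-arm comparison, such as the Eziclen total against the Klean-Prep preparation. The two arms' records must share one `ASPID` value; otherwise the BY puts them in separate panels.
3. Add `by ASPID;` with the matching sort to the per-country and the sex/age/weight PROC MIXED blocks, or restrict their WHERE clauses to the named record. One record per subject then enters each model, and the tables reconcile with the main compliance table.
4. State that panels containing one arm only (water, for example) are descriptive, with no treatment difference.

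The cost is a short definition and one line in each of two code blocks, with no new data and no protocol amendment. The downside is possibly more table panels and, in some cases, wider intervals. If the data already hold one record per subject, a clarifying sentence is enough.
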